### **Statement of Compliance to protocol, GCP and applicable regulatory guidelines:**

This trial will be conducted in compliance with the protocol, ISO 14155:2020, the International Council for Harmonization Good Clinical Practice E6(R2) (ICH GCP), Declaration of Helsinki, and all applicable regulatory requirements.

**Clinical Study Protocol**  
**Johnson & Johnson Vision Care, Inc.**

**CHANGE HISTORY**

Version	Originator	Description of Change(s) and Section Number(s) Affected	Justification for Change	Date
1.0	[REDACTED] [REDACTED]	Original Protocol	N/A	15 Jul 2021
2.0	[REDACTED] [REDACTED]	
 
• Study design change to create two (2) phases of the study           
 
○ Phase 1 added: verification of glare source intensity.
 
 
 
• Phase 2: is the same as protocol version 1.0 except 10 minute rest replaced with 5 minute rest.
 
• Section 1: added additional background information regarding glare source
 
• Section 1.1, 1.2, 1.4: Added Phase 1 details
 
• Section 1.5: added clarity to describe “broadband light source”, updated statements of results from previous studies
 
• Section 2.1, 2.2, 2.3: Added Phase 1 details
 
• Added Section 3.2.1 and 3.2.2 to specify Inclusion Criteria for Phase 1 and Phase 2
 
• Added Section 3.3.1 and 3.3.2 to specify Exclusion Criteria for Phase 1 and Phase 2
 
• Section 4.1, 4.2, 4.3: Added Phase 1 details
 
• Table 1 updated to include Phase 1 and update rest timings
 
• Section 5.1, 5.2: Added Phase 1 details
 
• Section 6: Added clarity that test article is for Phase 2 only
 
	
 
• Help ensure glare source emission meets ANSI Z80.12-2007
 
• Addition of Phase 1 study information throughout
 
• Additional specification for study information pertaining to Phase 1 or Phase 2
 
	4 Aug 2021

**Clinical Study Protocol**  
**Johnson & Johnson Vision Care, Inc.**

Version	Originator	Description of Change(s) and Section Number(s) Affected	Justification for Change	Date
		
 
• Section 6.4: update sample label
 
• Section 7.1: Added Phase 1 to Time and Events Schedule
 
• Section 7.2: Added Phase 1 Procedures, updated rest times in Phase 2 to match Table 1, updated step F.3 to remove “spectacle”
 
• Section 14.2: Added Phase 1 details
 
• Table 8: updated endpoint used
 
• Table 9: updated power analysis
 
• Section 14.5: Added Phase 1 details
 
• Section 14.6: clarification for Phase 2
 
• General formatting updates
 
		
3.0	[REDACTED] [REDACTED]	
 
• Section 1: added Figure 5 and the two sentences immediate before it. Updated subsequent figure numbers and text cross-references.
 
• Section 1.5: added comment that [REDACTED] and [REDACTED] used different control lenses.
 
• Section 2.3: reduced redundant language about going to phase 2 only after a successful phase 1.
 
• Section 7.2, Phase 1 step 1.12 and Phase 2 step 1.34 added ND filter for glare source in mesopic testing
 
• Section 7.2 Step 1.12: corrected exclusion language to be contrast sensitivity, not contrast sensitivity threshold.
 
	
 
• Additional information available regarding the glare source
 
• Updated to [REDACTED] Template v13.0
 
	30 Aug 2021

**Clinical Study Protocol**  
**Johnson & Johnson Vision Care, Inc.**

Version	Originator	Description of Change(s) and Section Number(s) Affected	Justification for Change	Date
		

• Corrected appendix numbering error (Appendix H was missing).

• Appendix I: Updated the Work Aid with glare source information and refined procedural steps.

• Appendix I added that includes Metropsis and glare specifics.

• Section 14.5 and 14.8: updated interim analysis language

• Updated to [REDACTED] Template v13.0

• Removed “Fellow Review” from Authorized Signatures section

		

# Clinical Study Protocol

## Johnson & Johnson Vision Care, Inc.

### SYNOPSIS

Protocol Title	Visual performance of senofilcon A with and without a new UV/HEV-filter
Sponsor	JJVC, [name]
Clinical Phase	Clinical trial phase: feasibility Design control phase: confirmatory phase
Trial Registration	This study will be registered on ClinicalTrials.gov by the Sponsor
Test Article(s)	Investigational Products: Test lens: senofilcon A with a new ultraviolet (UV) and High Energy Visible (HEV) light filter. Approved Products: Control lens: ACUVUE OASYS 1-Day (AO1D) (senofilcon A without a new UV/HEV-filter)
Wear and Replacement Schedules	Wear Schedule: daily wear Replacement Schedule: daily (non-dispensing study)
Objectives	The intent of this study is to demonstrate that the Test lens provides visual benefits under conditions for which it was designed. Primary Objectives: The primary objective is to evaluate the visual performance characteristics of a new HEV-filter under conditions of an HEV-rich ecologically-valid light source.
Study Endpoints	Phase 1: 

Primary endpoint(s): photopic and mesopic contrast sensitivity with and without glare.

 Phase 2: 

Primary endpoint(s): Photopic resolution acuity

Secondary endpoint(s): Mesopic contrast sensitivity, photopic contrast sensitivity

All primary and secondary endpoints will be assessed in the presence of an ecologically-valid broadband light source that emulates natural sunlight in spectral content across the visible spectrum.

# Clinical Study Protocol

## Johnson & Johnson Vision Care, Inc.

Study Design	
This study will occur in two non-dispensing phases:
 
Phase 1:
 

○ Approximately 20 subjects will be used to help ensure that the intensity of the glare source reduces the mean contrast sensitivity about 0.1 log units at 6 cpd (ANSI Z80.12 – 2007) under both photopic and mesopic conditions. This phase is a non-dispensing, non-randomized, controlled evaluation where subjects will wear their habitual contact lenses during testing. Subjects will be enrolled for approximately 1 hour.

 
Phase 2:
 

○ Approximately 60 different subjects will be used to evaluate the primary and secondary hypotheses of the study. This phase is a contralateral, non-dispensing, randomized, controlled, double-masked, study. Each subject will be contralaterally fitted with the two study articles during the single wearing period. Subjects will be enrolled for approximately 3 hours.

 
See the flow chart at the end of the synopsis table for the schematic of the study visits and procedures of main observations (Figure 1).

Sample Size	
Phase 1:
 

○ Up to 24 subjects will be enrolled to help ensure that 20 subjects complete phase 1 as cohort.

 
Phase 2:
 

○ Up to 66 subjects will be enrolled to help ensure that 60 subjects complete phase 2 as cohort.

Study Duration	
Phase 1:
 

○ The enrollment period will last approximately 1 week.

 
Phase 2:
 

○ The enrollment period will last approximately 8 weeks.

 
There will be an approximately one week pause between phase 1 and phase 2 for an interim analyses. Since this is a single-visit, non-dispensing study, the entire study duration (phase 1 + interim analysis + phase 2) will last approximately 10 weeks.

**Clinical Study Protocol**  
**Johnson & Johnson Vision Care, Inc.**

Anticipated Study Population	
Subjects must be habitual wearers of silicone hydrogel contact lenses worn on a daily wear basis. Subjects can be of any gender, race, and ethnicity that meet the eligibility criteria. Subjects enrolling in phase 1 or phase 2 will largely have the same eligibility criteria except where noted.
 
Subjects who participate in phase 1 of the study will not participate in phase 2 of the study.

Eligibility Criteria – Inclusion – PHASE 1	
Phase 1 Inclusion Criteria
 
Potential subjects must satisfy all of the following criteria to be enrolled in the study:
 
Inclusion Criteria following Screening
 
The subject must:
 
 
1. Read, understand, and sign the STATEMENT OF INFORMED CONSENT and receive a fully executed copy of the form.
 
2. Appear able and willing to adhere to the instructions set forth in this clinical protocol.
 
3. Be between 18-39 (inclusive) years of age at the time of screening.
 
4. By self-report, habitually wear spherical silicone hydrogel soft contact lenses in both eyes in a daily reusable or daily disposable wear modality (i.e. not extended wear modality). Habitual wear is defined as a minimum of 6 hours of wear per day, for a minimum of 5 days per week during the past 30 days.
 
5. Possess a wearable pair of spectacles that provide correction for distance vision.
 
6. Habitual spherical contact lens powers must be between -1.00 D and -6.00 D (inclusive) in each eye.
 
 
Inclusion Criteria following Baseline Evaluation
 
 
7. Habitual contact lenses must provide at least 20/20 acuity OD and OS
 

# Clinical Study Protocol

## Johnson & Johnson Vision Care, Inc.

Eligibility Criteria – Inclusion – PHASE 2	
Phase 2 Inclusion Criteria
 
Potential subjects must satisfy all of the following criteria to be enrolled in the study:
 
Inclusion Criteria following Screening
 
The subject must:
 

1. Read, understand, and sign the STATEMENT OF INFORMED CONSENT and receive a fully executed copy of the form.

2. Appear able and willing to adhere to the instructions set forth in this clinical protocol.

3. Be between 18 and 70 (inclusive) years of age at the time of screening.

4. By self-report, habitually wear spherical silicone hydrogel soft contact lenses in both eyes in a daily reusable or daily disposable wear modality (i.e. not extended wear modality). Habitual wear is defined as a minimum of 6 hours of wear per day, for a minimum of 5 days per week during the past 30 days.

5. Possess a wearable pair of spectacles that provide correction for distance vision.

 
Inclusion Criteria following Baseline Evaluation
 

6. The spherical equivalent of the subject's vertex-corrected distance refraction must be between -1.00 D and -6.00 D (inclusive) in each eye.

7. The magnitude of the cylindrical component of the subject's vertex-corrected distance refraction must be between 0.00 D and 1.00 D (inclusive) in each eye.

8. The best corrected, monocular, distance visual acuity must be 20/25 or better in each eye.

---	--

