### **5.3. Procedures for Maintaining and Breaking the Masking**

Every attempt will be made to keep the clinical trial personnel involved in the study (e.g. data management, biostatistician and clinical operations) unaware of the identity of the assigned study lenses. The identity of the study lenses will be masked by having the blister packs labeled with the study number, lot number, sphere power, expiration date and the randomization codes. Only the unmasked biostatistician generating the lens fitting schedule will have access to the decode information that allows matching of the randomization codes to the test articles. The medical monitor will also have access to the decode information in case breaking the mask is necessary for the urgent medical treatment of a subject.

Under normal circumstances, the mask should not be broken until all subjects have completed the study and the database is finalized. Otherwise, the mask should be broken only if specific emergency treatment/course of action would be dictated by knowing the treatment status of the subject. In such cases, the investigator may, in an emergency, contact the medical monitor. In the event the mask is broken, the sponsor must be informed as soon as possible. The date, time, and reason for the unmasking must be documented in the subject record. The investigator is also advised not to reveal the study treatment assignment to the clinical site or sponsor personnel.

Subjects who are discontinued will be replaced.

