**Clinical Study Protocol**  
**Johnson & Johnson Vision Care, Inc.**

Phase 2: Visit 1: Baseline		
Step	Procedure	Details
1.18	Entrance Visual Acuity	Record the distance Snellen visual acuity (OD, OS, and OU) to the nearest letter with their habitual spectacle. Subjects must read the smallest line until at least 50% of the letters are read incorrectly.
1.19	Subjective Sphero-cylindrical Refraction	Complete subjective sphero-cylindrical refraction and record the resultant distance visual acuity (OD, OS, and OU) to the nearest letter.
1.20	Eye Dominancy	The investigator will determine eye dominancy of the subject by first using the +1.00 blur test. If this fails to determine dominancy, then the sighting test will be used.
1.21	Slit Lamp Biomicroscopy	
FDA Slit Lamp Classification Scale will be used to grade the findings.
 
If any of these slit lamp findings are grade 3 or higher, the subject may not continue at this time, but may return up to one additional time to determine eligibility. If discontinued a final examination must be completed.
 
If the clearance of the fluorescein needs to be expedited, preservative-free rewetting drops or saline may be instilled.

1.22	Eligibility after Baseline	
All responses to Inclusion Criteria questions must be answered “yes” and all responses to Exclusion Criteria questions must be answered “no” for the subject to be considered eligible.
 
If subject is deemed to be ineligible after baseline, proceed to Final Evaluation and complete Subject Disposition. Refraction and Biomicroscopy forms do not need to be completed as part of Final Evaluation.

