**Clinical Study Protocol**  
**Johnson & Johnson Vision Care, Inc.**

Phase 2: Visit 1: Treatment 1 Lens Fitting		
Step	Procedure	Details
1.23	Lens Selection	
Assign the study lens based on the randomization scheme provided by the biostatistician.
 
Select the contact lens power [REDACTED] based on vertexed spherical equivalent from the refraction.

1.24	Lens Insertion	
The Investigator or the subject inserts the study lenses. Record the time of lens insertion.
 
Check for lens damage under the slit lamp before proceeding with lens settling.
 
Replace damaged lenses if applicable.
 
Ensure the subject is given a Patient Instruction Guide.

1.25	Lens Settling	Allow the study lenses to settle for a minimum of 5 minutes.
1.26	Subjective Best Sphere Over Refraction	Perform subjective best sphere refraction over the study lenses (adopt the maximum plus to maximum visual acuity (MPMVA) approach).
1.27	Lens Power Modification (if applicable)	
Adjust the lens power if the subject's best sphere over-refraction is not plano.
 
For each power modification, select the adjusted fitting lens power as appropriate and repeat steps 1.12 through 1.14.
 
Up to two power modifications are allowed per eye.

1.28	Subject Reported Ocular Symptoms	Subjects will respond to a verbal open-ended symptoms questionnaire.
1.29	Visual Acuity	Record the best corrected Snellen distance visual acuity to the nearest letter (OD and OS). Subjects must read the smallest line until at least 50% of the letters are read incorrectly. Visual acuity with the study contact lenses must be 20/30 or better OD and OS.

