**Clinical Study Protocol**  
**Johnson & Johnson Vision Care, Inc.**

Phase 2: Visit 1: Treatment 1 Lens Fitting		
Step	Procedure	Details
1.30	General Lens Fit Assessment	
Evaluate lens centration, movement on blink, and push-up test for each eye.
 
An unacceptable fit is deemed by one of the following criteria:
 
 
• limbal exposure at primary gaze or with extreme eye movement.
 
• edge lift.
 
• excessive movement in primary and up gaze.
 
• insufficient movement in all three of the following conditions: primary gaze, up gaze, and push-up test.
 
 
Note: if lens fit is unacceptable for either eye, the subject will be discontinued from the study.

1.31	Continuance	
For the subject to continue in the study, they must meet all three of the following criteria:
 
 
1. Visual acuity is 20/30 or better OD and OS.
 
2. The lens fit is acceptable OD and OS.
 
3. Investigator approval.
 
 
If the Investigator does not approve the study lens, then the study is terminated for that subject.

1.32	Lenses Worn in Clinic	
The lenses will be released for approximately two hours.
 
 
1. The subjects must wear both study lenses the entire time.
 
2. The lenses will be worn as daily wear only.
 
3. Rewetting drops are permitted if needed.
 
 
Note: In the event a lens is lost or damaged, it will be replaced immediately.
 
Note: A clinic-only-wear Patient Instruction Guide will be provided.

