#### Photopic Resolution Acuity using Landolt C's with a Glare Source

The photopic resolution acuity using Landolt C's (converted to logMAR unit using  $logMAR = log_{10}(arcminute)$ ) will be analyzed under bright light conditions with a broadband light source (glare) using a linear mixed model with a normal distribution. Lens type, dominant eye, and the interaction of lens type by dominant eye will be included in the model as fixed effects and age as a covariate. The covariance of residuals between eyes within the same subject (R-side) will be modeled using Unstructured (UN) covariance structure. If the model does not converge, then a compound Symmetry (CS) covariance structure will be considered. The Kenward and Roger method (Kenward and Roger, 1997) will be used for the denominator degrees of freedom.

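### The Phase 2 models leave out each eye's uncorrected cylinder, which is measured before lens assignment; this forgoes some precision in the contralateral comparison but causes no bias

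*Combined protocol and SAP*

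**What the plan says.** - **Eligibility.** Phase 2 inclusion criterion 7 (Synopsis and Section 3.2.2) requires that the "cylindrical component of the subject's vertex-corrected distance refraction must be between 0.00 D and 1.00 D (inclusive) in each eye". It applies to each eye separately. No criterion concerns the difference between eyes.
- **Lens power.** Step 1.23 of Section 7.2 selects the power "based on vertexed spherical equivalent from the refraction". Step 1.26 refines it by sphere only: "Perform subjective best sphere refraction over the study lenses". Section 5.3 describes "blister packs labeled with the study number, lot number, sphere power, expiration date and the randomization codes", with no cylinder or axis, and Table 2 lists neither.
- **Measurement.** Step 1.19 reads "Complete subjective sphero-cylindrical refraction and record the resultant distance visual acuity (OD, OS, and OU) to the nearest letter". It comes before lens assignment at step 1.23, and Section 5.1 requires baseline information to be collected before randomisation.
- **Continuance.** Step 1.31 requires, with the study lenses in place, "Visual acuity is 20/30 or better OD and OS".
- **Model.** In Section 14.5, lens type, dominant eye and their interaction "will be included in the model as fixed effects and age as a covariate". Section 14.6 uses the same terms for the photopic area under the log contrast sensitivity function (AULCSF) and analyses mesopic AULCSF the same way. No refractive term appears.

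**The concern.** The Test-minus-Control contrast is a difference between two eyes of one person, so anything that differs between those eyes apart from the lens enters as noise. Uncorrected cylinder blurs the image, the primary endpoint is a resolution task, and the target difference is only 0.05 logMAR. The primary result also gates both secondary tests.

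Nothing now in the plan takes this noise out:
- Age is constant within a subject.
- Dominance is the only eye-level covariate, and it does not carry refraction.
- The unstructured residual covariance estimates how strongly the eyes agree, but it cannot recover variance due to a measured covariate that was left out.
- The entry acuity in criterion 8 is best-corrected, so it is taken with the cylinder neutralised.

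What is at stake is the width of the interval for the lens effect.

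**Working it through.** **1. Reproduce the plan's figure.** The inputs are in Section 14.2 and Table 9: primary difference 0.05 logMAR, two-sided alpha 0.05, paired t-test (exact), 60 completers. The variance of the between-eye difference is V = s_T² + s_C² − 2·r·s_T·s_C.

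- SDs 0.10/0.11, r 0.3: 0.0100 + 0.0121 − 0.0066 = 0.0155
- SDs 0.10/0.11, r 0.5: 0.0100 + 0.0121 − 0.0110 = 0.0111
- SDs 0.08/0.09, r 0.3: 0.0064 + 0.0081 − 0.00432 = 0.01018
- SDs 0.08/0.09, r 0.5: 0.0064 + 0.0081 − 0.0072 = 0.0073

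Noncentral t power with noncentrality 0.05/√(V/60) and 59 df gives 86.4%, 95.1%, 96.5% and 99.4%. These match Table 9.

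**2. Assumptions that the documents do not supply.** The loss k is 0.10 to 0.20 logMAR per dioptre of uncorrected cylinder. The SD of the between-eye cylinder difference is 0.20 to 0.30 D. Table 9's SDs already contain this noise.

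**3. Variance attributable to cylinder.** This is (k × SD)².

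- Low end: (0.10 × 0.20)² = 0.0004
- High end: (0.20 × 0.30)² = 0.0036

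**4. Power after adjustment.** Replace V by V minus that amount.

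| Table 9 row (n = 60) | Share of V removed | Power: plan → adjusted |
|---|---|---|
| 0.10/0.11, r 0.3 | 2.6% to 23% | 86.4% → 87.3% to 93.7% |
| 0.10/0.11, r 0.5 | 3.6% to 32% | 95.1% → 95.7% to 99.3% |
| 0.08/0.09, r 0.3 | 3.9% to 35% | 96.5% → 97.1% to 99.7% |
| 0.08/0.09, r 0.5 | 5.5% to 49% | 99.4% → 99.6% to 100% |

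With 58 df instead of 59, to pay for the covariate, the first row still prints as 87.3% and 93.7%. In subjects, the first row's gain equals 60 × 0.0155/0.0151 − 60 ≈ 2 extra completers at the low end and 60 × 0.0155/0.0119 − 60 ≈ 18 at the high end.

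**5. A second set of assumptions.** Take cylinder uniform over 0, 0.25, 0.50, 0.75 and 1.00 D (SD 0.354 D per eye) with between-eye correlation 0.5, so the SD of the difference is also 0.354 D. With k = 0.05, 0.10 or 0.15, and the noise again inside Table 9's SDs, power moves from 86.4% to 87.1%, 89.1% or 92.2%, and from 96.5% to 97.0%, 98.1% or 99.3%.

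**6. Bias and type I error.** A simulation of 40,000 trials used 60 subjects, blocks of two, a systematic right/left imbalance in cylinder, and k from 0 to 0.20. It gave mean bias 0.000 logMAR and two-sided type I error of 4.1% to 4.9%.

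The documents give no basis for a slope of AULCSF on cylinder, so no figure is offered for the secondary endpoints.

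**The case against.** The strongest reply is that nothing here is invalid. Randomising the eye protects the comparison, the plan prespecifies a reasonable model, and almost any eye-level variable could be urged on the same grounds. The size rests wholly on outside inputs. At the low end the gain is under one power point, and every primary row at 60 completers already exceeds 86%. All of that stands. What sets cylinder apart is that it is a known source of blur in an acuity task, left uncorrected by design and determined before lens assignment.

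Four stronger readings are tempting, and the documents do not support them:

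- **That Table 9 overstates power.** Its SDs and correlations are total-variance assumptions, and correlations of 0.3 to 0.5 already allow considerable disagreement between eyes. If cylinder noise came on top of them, the second set of assumptions would lower 86.4% to 85.8%, 83.7% or 80.4%. Nothing shows that it was left out.
- **That unequal cylinder defeats the design rationale.** Section 4.2 cites light sensitivity, iris colour, macular pigment and consistent threshold criteria. It does not claim equal refraction.
- **That the extreme pair, 0 against 1.00 D, is typical.** It would differ by 0.10 to 0.20 logMAR, two to four times the target effect. But criterion 4 admits only habitual wearers of spherical lenses, and each eye must reach 20/30 (log10(30/20) = 0.176 logMAR) with the study lens. At 0.20 logMAR per dioptre, an eye with 1.00 D passes only if its corrected acuity is better than 0.176 − 0.20 = −0.024 logMAR. This gate trims the extreme without equalising the eyes.
- **That eligibility should cap the between-eye difference.** The 1.00 D limit agrees with the Control lens indication in Appendix C. Any cap would be arbitrary and would add screen failures, which count as enrolled (Section 4.3) and so draw on the margin of 66 for 60.

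**Conclusion.** The point holds as a missed gain in precision. Cylinder of up to 1.00 D per eye is left uncorrected, may differ between eyes, is determined before lens assignment, and is absent from all three Phase 2 models. The lens effect is neither biased nor tested at the wrong level, and Table 9 reproduces.

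The gain depends on the assumed loss per dioptre and on the spread of between-eye cylinder, and it presumes that Table 9's SDs already include this noise. On those terms it runs from under 1 to about 7 power points in the least favourable primary row (86.4% to 87.3–93.7%). It is smaller in power points in the other rows, which start at 95% or more. An effect on AULCSF is plausible but not quantified. The case for acting is that the cost is close to nothing and that the covariate must be named in advance: adding it after unmasking would be a post-hoc choice of model.

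**What to change.** In Section 14.5, add each eye's refractive cylinder magnitude from step 1.19 as an eye-level covariate in the photopic resolution acuity model. For consistency, do the same in both AULCSF models in Section 14.6. Use the pre-assignment refraction; acuity without glare through the study lens is measured after randomisation and would be a less clean covariate.

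The cost is one degree of freedom and a sentence in each section. Step 1.19 names only the acuity as the recorded item, so confirm that the refraction form captures cylinder for each eye; criterion 7 cannot be checked without it. No change to eligibility, sample size or procedures is needed.
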